3.7.1.5.4 Fourth Day of Administration at Reduced Dose

The investigator or subinvestigator will perform the following procedures.

1) Before tolvaptan administration

The investigator or subinvestigator will perform the following examinations, and then, offer breakfast to the subject.

- Body weight
- Serum or blood sodium concentration
- Serum or blood potassium concentration
- Plasma AVP concentration (only subjects from whom samples are available)
- Plasma drug concentration: Assessment after breakfast is allowed if it is conducted prior to tolvaptan administration.

The investigator or subinvestigator will instruct the subject to completely discharge the urine immediately after breakfast, and start urine collection and fluid intake measurement to assess the following items.

- Daily urine volume
- Daily fluid intake
- Daily fluid balance
- Urine sodium excretion
- Urine potassium excretion
- Urine osmolality

2) Tolvaptan administration

The investigator or subinvestigator will instruct the subject to take tolvaptan with water after breakfast according to [Section 3.2](#).

3) At a feasible time

- Vital signs
- 12-lead ECG
- Edematous symptoms (after tolvaptan administration)
- Chest x-ray
- Concomitant drugs and therapies
- IMP compliance
- Adverse events

3.7.1.5.5 Day After Final Administration in Extended Treatment at Reduced Dose

The investigator or subinvestigator will perform the following procedures.

1) Before breakfast

- Body weight
- Laboratory tests (Assessment will not be performed if it is completed on the previous day.)
- Serum or blood sodium concentration
- Serum or blood potassium concentration

- Serum osmolality (Assessment will not be performed if it is completed on the previous day.)
- Plasma AVP concentration (on the day after the third day of administration at reduced dose; only subjects from whom samples are available)
- Plasma drug concentration (on the day after the third day of administration at reduced dose)
 - : Assessment after breakfast is allowed if it is conducted prior to tolvaptan administration.

2) At a feasible time

- Vital signs
- 12-lead ECG (on the day after the third day of administration at reduced dose)
- Edematous symptoms
- Chest x-ray (on the day after the third day of administration at reduced dose)
- Concomitant drugs and therapies
- Adverse events

3.7.1.5.6 Two Days After Final Administration in Extended Treatment at Reduced Dose

The investigator or subinvestigator will perform the following procedures.

1) At a feasible time

- Vital signs
- Concomitant drugs and therapies
- Adverse events

3.7.1.6 Treatment Discontinuation

When discontinuation of treatment with tolvaptan is deemed necessary according to the rules specified in [Section 3.8.3.1](#), the investigator or subinvestigator will perform the following examinations or investigations. If the examination or investigation has been completed on the day of treatment discontinuation, it does not have to be repeated. If it is not feasible to perform all of the examinations, observations, and assessments at treatment discontinuation, because of the subject's refusal or at the discretion of the investigator or subinvestigator (eg, in emergencies), only feasible ones should be performed.

- Concomitant drugs and therapies
- Serum or blood sodium concentration
- Serum or blood potassium concentration

- Body weight
- Laboratory tests
- Serum osmolality
- Plasma drug concentration (Assessment does not have to be repeated on the day of treatment discontinuation if it has been conducted after administration.)
- Vital signs
- 12-lead ECG
- Edematous symptoms
- IMP compliance
- Adverse events

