3.7.1.3.1 Day 1 of Treatment Period

The investigator or subinvestigator will perform the following procedures.

1) Before tolvaptan administration

The investigator or subinvestigator will perform the following examinations, and then, offer breakfast to the subject.

- Body weight
- Serum or blood sodium concentration
- Serum or blood potassium concentration

The investigator or subinvestigator will instruct the subject to completely discharge the urine immediately after breakfast, and start urine collection and fluid intake measurement to assess the following items.

- Daily urine volume
- Daily fluid intake

- Daily fluid balance
- Urine sodium excretion
- Urine potassium excretion
- Urine osmolality

2) Tolvaptan administration

The investigator or subinvestigator will instruct the subject to take tolvaptan (0.05 mg/kg/day) with water after breakfast. After administration, the change in serum or blood sodium concentration will be observed. If the change meets the following criteria, the investigator or subinvestigator should discontinue treatment with tolvaptan as specified in [Section 3.8.3.1](#), and perform the withdrawal examination according to [Section 3.7.1.6](#).

- Serum or blood sodium concentration increased by ≥ 8 mEq/L from that immediately before tolvaptan administration, within 8 to 12 hours after administration
- Serum or blood sodium concentration increased by ≥ 12 mEq/L from that immediately before tolvaptan administration, within 24 hours after administration
- Serum or blood sodium concentration exceeding 145 mEq/L is observed during the treatment period

3) 4 to 6 hours after tolvaptan administration

- Serum or blood sodium concentration

4) 8 to 12 hours after tolvaptan administration

- Serum or blood sodium concentration

5) At a feasible time

- Vital signs
- Edematous symptoms (after tolvaptan administration)
- Concomitant drugs and therapies
- IMP compliance
- Adverse events

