3.7.1.3.3 Day 3 of Treatment Period

The investigator or subinvestigator will perform the following procedures.

1) Before tolvaptan administration

The investigator or subinvestigator will perform the following examinations, and then, offer breakfast to the subject.

- Body weight
- Serum or blood sodium concentration
- Serum or blood potassium concentration
- Plasma drug concentration (on the third day of administration at 0.05 mg/kg/day)

Assessment after breakfast is allowed if it is conducted prior to tolvaptan administration.

The investigator or subinvestigator will instruct the subject to completely discharge the urine immediately after breakfast, and start urine collection and fluid intake measurement to assess the following items.

- Daily urine volume
- Daily fluid intake
- Daily fluid balance
- Urine sodium excretion
- Urine potassium excretion
- Urine osmolality

2) Tolvaptan administration

The investigator or subinvestigator will instruct the subject to take tolvaptan with water after breakfast according to [Section 3.2](#).

- 3) 2 to 4 hours after tolvaptan administration (on the third day of administration at 0.05 mg/kg/day)
 - Plasma drug concentration
- 4) 4 to 6 hours after tolvaptan administration (at increased dose)
 - Serum or blood sodium concentration
- 5) 8 to 12 hours after tolvaptan administration (at increased dose)
 - Serum or blood sodium concentration
- 6) 10 to 14 hours after tolvaptan administration (on the third day of administration at 0.05 mg/kg/day)
 - Plasma drug concentration
- 7) At a feasible time
 - Vital signs
 - Edematous symptoms (after tolvaptan administration)
 - Concomitant drugs and therapies
 - IMP compliance
 - Adverse events

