3.7.1.3.10 Day After Final Administration

If administration at the dose decided for each individual subject is completed in 3 days, the investigator or subinvestigator will perform the following procedures on the day after final administration.

1) Before breakfast

- Body weight
- Laboratory tests
- Serum or blood sodium concentration
- Serum or blood potassium concentration
- Serum osmolality
- Plasma AVP concentration (only subjects from whom samples are available)

- Plasma drug concentration: Assessment after breakfast is allowed.
- 2) At a feasible time
 - Vital signs
 - 12-lead ECG
 - Edematous symptoms
 - Chest x-ray
 - Concomitant drugs and therapies
 - Adverse events

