3.7.2 Efficacy Assessments

3.7.2.1 Body Weight

A calibrated scale (an instrument which can measure body weight to the second decimal point by the kilogram) should be used to determine body weight while minimizing the influence of clothing, at about the same time before breakfast throughout the trial period. The date and time, and result of measurement (to the second decimal point by the kilogram) will be recorded in a source document and a CRF. The result should be rounded to 2 decimal places.

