## **5.6 Handling of Missing Data**

If data on body weight and edematous symptoms cannot be obtained for assessment on (the day after) the third day of administration at the evaluation dose, the missing data will be imputed using the last available data obtained by that day.

If data on body weight on the day after the third day of administration at the evaluation dose cannot be obtained for the primary endpoint, the definition of the primary endpoint, “the mean daily urine volume for the 3 days of treatment at the evaluation dose” ([Section 6.1](#)), will be changed to “the mean daily urine volume from the start of administration at the evaluation dose to the day on which the imputed data on body weight is obtained.”

If data on body weight, edematous symptoms, and safety endpoints cannot be obtained even on the day of (or the day after) the final administration at the evaluation dose and the day of (or the day after) the final administration, the missing data will be imputed using the last previous data obtained.

The missing data will be imputed when there are data after the administration at the evaluation dose for (the day after) the third day of administration at the evaluation dose and the day of (or the day after) the final administration at the evaluation dose, or after the IMP administration for the day of (or the day after) the final administration (‘after the administration at the evaluation dose’ for the analysis with baseline as the first day or immediately before the start of administration at the evaluation dose).

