## **5.7 Definition of Evaluation Dose**

Of the doses administered as specified in [Section 3.2.2](#) and [Section 3.2.3](#), the dose meeting the following criteria is defined as an evaluation dose.

- 1) If sufficient increase in urine volume was obtained during the course of dose escalation, or if the dose was increased to 0.5 mg/kg/day because sufficient increase in urine volume was not obtained:
  - If the dose was not subsequently reduced, then that dose
  - If the dose was reduced without having been administered for 3 days, then the reduced dose
  - If the dose was reduced after having been administered for 3 days, then the dose before reduction

- 2) If IMP administration was discontinued before sufficient increase in urine volume was obtained during the course of dose increase:
  - The dose at final IMP administration

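### A child stopped on the first dosing day of a dose step may have no usable weight for the primary endpoint, and the plan does not say how that child is counted

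*Protocol*

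**What the plan says.** **Weighing and dosing.** Protocol 3.7.2.1 has weight taken "at about the same time before breakfast throughout the trial period". Protocol 3.2.1 places the dose after breakfast. A weight taken on a dosing day is therefore a predose weight.

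**Withdrawal examination (protocol 3.7.1.6).** Body weight is on the list. The general waiver reads "If the examination or investigation has been completed on the day of treatment discontinuation, it does not have to be repeated". Only the plasma drug concentration carries a postdose condition: "Assessment does not have to be repeated on the day of treatment discontinuation if it has been conducted after administration". Daily urine volume is not on the list.

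**Weight on the morning after the last dose (protocol 3.7.1.3.10).** This visit applies "If administration at the dose decided for each individual subject is completed in 3 days". The next weight scheduled for a child who stops earlier is at follow-up, 5 to 7 days after the last dose (3.7.1.7).

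**Same-day triggers.** Sodium is drawn 4 to 6 h and 8 to 12 h after dosing on Day 1 and again on the day of each increase (Days 3, 5 and 7). One discontinuation criterion is: "Serum or blood sodium concentration increased by ≥ 8 mEq/L from that immediately before tolvaptan administration, within 8 to 12 hours after administration".

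**Evaluation dose (protocol 7.4, SAP 5.7).** If treatment stops before a sufficient urine increase, it is "The dose at final IMP administration".

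**Missing weights.** Protocol 7.3 carries forward the last value available by the day after the third day at the evaluation dose. SAP 5.6 adds a restriction: "The missing data will be imputed when there are data after the administration at the evaluation dose". SAP 3.4 excludes values from unscheduled visits.

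**The concern.** The within-day sodium samples fall on the first day of each dose step, which is the day when the only weight at that dose was taken before the dose. A child stopped that day has met the weight item of the withdrawal examination without ever being weighed under the dose on which the primary endpoint is to be judged.

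The endpoint can then go missing for a reason tied to response and safety: these children stop because sodium rose too far or because of another safety finding. If they drop out of the percentage, the responder rate describes children who got past the first day of their step. If the predose weight is carried forward instead, they are scored on a weight that reflects a lower dose or, on Day 1, on the baseline itself. The documents do not settle which of these happens. The postdose condition on the drug-concentration item shows that the distinction was recognised there but was not applied to the weight.

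**Working it through.** **1. Timing.** For a stop on Day d, the first day at a step, the endpoint weight is due on the day after the third day at that dose, d + 3. Follow-up falls on d + 5 to d + 7.

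| Step (mg/kg/day) | Stop day d | Endpoint day d + 3 | Follow-up days | Last scheduled weight by endpoint day |
|---|---|---|---|---|
| 0.05 | 1 | 4 | 6–8 | Day 1 predose, which is the baseline |
| 0.15 | 3 | 6 | 8–10 | Day 3 predose, reflecting 0.05 |
| 0.3 | 5 | 8 | 10–12 | Day 5 predose, reflecting 0.15 |
| 0.5 | 7 | 10 | 12–14 | Day 7 predose, reflecting 0.3 |

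Follow-up starts at least 2 days after the endpoint day, so it can never be the last value available by that day.

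**2. The two missing-data rules applied to the Day 3 case.** The evaluation dose is 0.15 mg/kg/day.
- Protocol 7.3: the Day 3 predose weight is carried forward and the child is scored.
- SAP 5.6: no weight follows administration at 0.15 mg/kg/day by Day 6, so nothing is imputed and the child has no value.
- SAP 14 lists a change to protocol 7.3, but only to align the assessment days for edematous symptoms. It does not list this restriction.

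**3. Analysis set.** The full analysis set needs a postdose weight and a postdose urine volume. Children stopped on Day 3, 5 or 7 can qualify through data at lower doses. For a Day 1 stop, membership depends on whether the follow-up weight counts and on whether a postdose urine volume exists. Neither document gives a counting rule for a child in the set without a value.

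**4. The plan's own figure.** The exact lower limit for x of n is the 0.025 quantile of Beta(x, n − x + 1). Find the smallest x whose limit exceeds 0.3, then the binomial probability of reaching it.
- p = 0.5: n = 68 needs 29 (limit 0.307), probability 0.909. The 90% level is first reached at n = 66 and holds for every n from 68.
- p = 0.6: n = 30 needs 15 (limit 0.313), probability 0.903.

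Both stated sizes, 68 and 30, reproduce. At the planned 60 the boundary is 26 (limit 0.306), with probability 0.878 at p = 0.5 and 0.997 at p = 0.6.

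**5. What the missing counting rule could do.** The number k of such children is not in the documents, so 0 to 6 is assumed. At p = 0.5 among scorable children, the probability that the lower limit exceeds 0.3 is:

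| k | Excluded | Counted as non-responders |
|---|---|---|
| 0 | 0.878 | 0.878 |
| 1 | 0.851 | 0.851 |
| 2 | 0.882 | 0.821 |
| 3 | 0.855 | 0.787 |
| 4 | 0.825 | 0.748 |
| 6 | 0.830 | 0.658 |

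The excluded column is not monotone because the boundary count is an integer.

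Illustration with 25 responders: the lower limit is 29.1% for 25/60, 29.6% for 25/59 and 30.2% for 25/58. With 33 responders the rate is 33/60 = 55.0%, and 33/57 = 57.9% if three are excluded.

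**The case against.** **Many stops will leave a usable weight.** Sodium is also drawn before breakfast every day, together with a weight. On Days 2, 4, 6 and 8 that sample serves the 24-hour criterion, and a value above 145 mEq/L can appear on any morning. A stop decided then has a weight about 24 hours after the evaluation dose. The protocol does not define the day of discontinuation for a once-daily drug, so a site might treat an evening decision as effective next morning. This stands, and it confines the point to stops made on the dosing day itself.

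**The child stays in hospital and is followed.** Protocol 3.2.6 plans admission until 2 days after the last dose, and 3.8.3.3 asks for continued assessments where possible. A site may well reweigh. But no next-morning weight is scheduled for a child stopped early, and SAP 3.4 would drop an unscheduled one.

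**The urine part is weaker.** Protocol 3.5.1 covers urine up to discontinuation, 3.7.2.2 runs each collection to the next morning, and footnote b of Table 3.7-1 extends a measurement to the morning after the last dose. The table body could not be read here, so the scope of that footnote is not judged. What stands is that the withdrawal list does not itself ask for the collection to be completed.

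**Stronger readings that a reader might infer, and that the documents do not support:**
- *Postdose potassium at the stop is lost as well.* Laboratory tests are not scheduled on Days 1, 3, 5 or 7, so the waiver does not cover them. They are due at withdrawal, and the chemistry panel in Table 3.7.3.2-1 includes potassium.
- *The child cannot be scored at all.* That follows from SAP 5.6 only; protocol 7.3 would score the child.
- *The responder rate is biased upward.* That requires exclusion from the denominator, which no section states. Counted as non-responders, the children leave 25/60 unchanged.
- *Two such children would turn a failed trial into a successful one.* The 0.3 value is a sample-size input. The plan sets no pass/fail rule and assesses efficacy comprehensively. The count of 25 was chosen at the boundary; 26/60 already gives a limit of 30.6%.

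**Conclusion.** The concern holds in a limited form. For a child stopped on the first dosing day of a step, before a sufficient urine increase, the protocol does not secure a weight that reflects the evaluation dose by the endpoint day. The two documents then give different treatments, and neither says how the child is counted. The missingness is informative because it follows safety stops.

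Its size cannot be stated, since the documents give no rate for such stops. The effect on the lower limit (29.1% against 30.2% for 25 responders and two children) shows only that the choice of denominator can matter near the planning threshold, and it assumes exclusion. There is no error in the sample-size calculation. The plan should be changed because the gap touches the primary endpoint and is cheap to close.

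**What to change.** - **Protocol 3.7.1.6:** for discontinued subjects, require a pre-breakfast weight on the morning after the last dose, and completion of the urine collection already running to that morning. A morning weight keeps to the timing in 3.7.2.1; an evening repeat would not. There is no need to repeat the other items after the dose, which would add blood draws in children.
- **SAP 3.4:** map both values to the primary-endpoint time point so that they are not dropped as unscheduled. That section already says how withdrawal-examination sodium is handled.
- **SAP 5.6 and protocol 7.3:** reconcile them into one rule on whether a weight from before the evaluation dose may be carried forward, and record the change in SAP 14.
- **Counting rule:** treated children who still have no weight after the evaluation dose count as non-responders in the primary analysis, including Day 1 stops whose place in the full analysis set is unclear. Give exclusion as a sensitivity analysis. The rule is needed even with the extra weighing, because 3.7.1.6 allows items to be omitted on refusal or in an emergency.
- **Stopping rules:** unchanged.

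The cost is a short protocol amendment and SAP update, plus one weighing and the end of a running collection in discontinued children who are already planned to be in hospital. The responder rate may come out slightly lower. With two children counted as non-responders, the planning probability at p = 0.5 would be 0.821 rather than 0.878.

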3.7.1.7 Follow-up Period (5 to 7 Days After Final Tolvaptan Administration)

The investigator or subinvestigator will perform the following procedures.

- 1) At a feasible time
 - Body weight
 - Vital signs
 - 12-lead ECG
 - Laboratory tests
 - Serum or blood sodium concentration
 - Serum or blood potassium concentration
 - Serum osmolality
 - Edematous symptoms
 - Concomitant drugs and therapies
 - Adverse events

3.7.2 Efficacy Assessments

3.7.2.1 Body Weight

A calibrated scale (an instrument which can measure body weight to the second decimal point by the kilogram) should be used to determine body weight while minimizing the influence of clothing, at about the same time before breakfast throughout the trial period. The date and time, and result of measurement (to the second decimal point by the kilogram) will be recorded in a source document and a CRF. The result should be rounded to 2 decimal places.

3.7.2.2 Daily Urine Volume

During the pretreatment observation period, daily urine volume will be measured for the time interval starting at urination (an instruction to urinate) after breakfast and ending at complete urination immediately before administration on the following day. After start of tolvaptan administration on the first day of the treatment period, daily urine volume will be determined for each time interval from the point after urination (an instruction to urinate) immediately before administration of the day to the point after urination (an instruction to urinate) immediately before administration on the following day.

For diapered subjects whose urine volume is difficult to determine by urine collection, urine volume may be estimated from the difference in the weight of diaper between before and after use (the weight at 1 g should be converted to 1 mL). The procedure should be established with consideration of measurement time to minimize fluctuations. The method of urine volume measurement (urine collection, diaper, or both) should not be changed throughout the trial period.

The status (measured/not measured), start date and time, and completion date and time of measurement, as well as daily urinary volume will be recorded in a source document and a CRF.

3.7.2.3 Edematous Symptoms (Edema [Lower Limbs, Eyelids, etc], Dyspnea, Jugular Venous Distension, Respiration Rate at Rest, and Pulse Rate)

3.7.2.3.1 Edema (Lower Limbs, Eyelids, etc)

3.7.2.3.1.1 Edema (Lower Limbs)

In principle, the grade of edema at the tibial border or the acrotarsium will be assessed in the sitting position, according to Table 3.7.2.3.1.1-1. The date and time, and result of assessment will be recorded in a source document and a CRF.

Table 3.7.2.3.1.1-1 Criteria for Grading Lower Limb Edema

	Grade	Criterion
0	None	No pit observed
1	Mild	Faint pit observed
2	Moderate	Pit observed
3	Severe	Easily recognizable edema

3.7.2.3.1.2 Edema (Eyelids)

The presence/absence of eyelid edema will be assessed. The date and time, and result of assessment will be recorded in a source document and a CRF.

3.7.2.3.1.3 Edema (Others)

The same criteria as those for lower limb edema will be adopted to assess other edema. The same area of the body will be assessed before and after administration. The area, date and time, and result of assessment will be recorded in a source document and a CRF.

